#### • Physical exercise:

- I have not done any kind of physical exercise
- I have done at least 45 minutes of physical exercise 2-3 days a week
- I have done 45 min of physical exercise 4-5 days a week for at least 6 months
- I have done at least 45 minutes of physical exercise every day

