Some authors recommend training with aerobic exercises for 30 minutes 3 times a week. Randomised clinical trials have demonstrated better responses in oncology patients using resistance training. It is important to take into account the patients' previous level of activity and cardiac output before recommending exercise.

In view of the above, we believe it is appropriate to initiate a study to prospectively assess fatigue-related quality of life in patients with mRCC who are starting treatment with a tyrosine kinase inhibitor.

The patients' quality of life will be evaluated using the FACIT-Fatigue questionnaire and a Patient Diary (both to be completed by the patient) every 6 weeks.

To our knowledge, no fatigue-related quality of life studies in European patients with this condition have been published to date.

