#### LIFESTYLE (weekly from baseline visit to month 9)

- 1) Napping
- 2) Aerobic exercise
- 3) FACIT Fatigue questionnaire score at the scheduled visits

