#### ✓ Smoking

- o No
- o Yes
- o Occasional
- $\circ$  Former smoker of <6 months
- ✓ Dose of the tyrosine kinase inhibitor and regimen with which they initiated treatment at baseline visit
  - Sunitinib 50 mg 4/2 regimen
  - Sunitinib 50 mg 2/1 regimen
  - o Sunitinib 37.5 mg 4/2 regimen
  - Sunitinib 37.5 mg 2/1 regimen
  - Sunitinib 25 mg 4/2 regimen
  - Sunitinib 25 mg 2/1 regimen
  - Pazopanib 800 mg/24 hours continuous
  - Pazopanib 400 mg/24 hours continuous
  - Sorafenib 400 mg/24 hours continuous
  - Sorafenib 400 mg/12 hours continuous

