## 8.2.3 Follow-up analysis

The evolution of the following aspects will be presented for each one of the follow-up visits of the patients at which the variables listed below are recorded:

- Presence of palmar-plantar erythrodysesthesia: the absolute and relative frequency of patients who as of month 3 of treatment develop palmar-plantar erythrodysesthesia of any grade will be provided. In the sub-population of patients with hand-foot syndrome, the frequency distribution will be presented according to the degree of severity of these AE, according to CTCAE (Common Terminology Criteria form Adverse Event) version 4:
  - o Grade 1
  - o Grade 2

#### o Grade 3

For each one of the evolution visits (month 6 and month 9), a study will be performed to ascertain whether significant changes have occurred in the presence and the grade of the HFS with regard to the previous visit, defined as (improved, maintained or worsened). The Pearson chi-squared test will be used for this purpose (or Fisher's exact test for 2x2 tables or likelihood ratio test for mxn tables, if necessary).

- Presence of fatigue: the absolute and relative frequency of patients with the presence of fatigue of any degree since the baseline visit will be provided. In the sub-population of patients with fatigue, the frequency distribution will be presented according to the degree of severity, according to CTCAE (Common Terminology Criteria form Adverse Event) version 4:
  - o Grade 1
  - o Grade 2
  - o Grade 3
  - o Grade 4

For each one of the evolution visits (month 3, month 6 and month 9), a study will be performed to ascertain whether significant changes have occurred in the grade of fatigue with regard to the previous visit, defined as (improved, maintained or worsened). Significant associations will be sought between the habits of daytime rest, physical aerobic exercise, medication taken, dose and treatment schedule changes, dose interruptions and the number of days of treatment interruption depending on the evolution of the presence and degree of fatigue in the last twelve weeks. The Pearson Chi-squared test will be used for this purpose (or Fisher's exact test for 2x2 tables or likelihood ratio test for mxn tables, if necessary).

- Patient diary data (weekly): the distribution of patient frequencies will be presented according to the following habits:
  - Napping
    - Every day
    - Weekend and/or holidays
    - Sporadically, between 2 or 6 days
    - Has not taken a nap any day

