## • Has taken the medication:

- In the morning (between 7 am and 12 noon)
- In the afternoon (between 1 pm and 7 pm)
- At night (between 8 pm and 6 am)
- I have not taken any medication this week

For each one of the weekly habits described above, a summary calculation will be made (after three months) of each patient's habits in terms of daytime rest, physical exercise and taking their medication, taking the options marked with greater frequency in the last 12 weeks into account.

FACIT\_Fatigue: The main measures of centrality and dispersion measures will be calculated (mean, standard deviation, median, minimum, maximum, IR and 95%CI ) from the score obtained in the FACIT\_Fatigue quality of life scale, calculated as described in ANNEX 1. The absolute and relative frequency of patients with severe fatigue, being those with a score of less than 30 points on the FACIT\_Fatigue scale, will also be presented.

For each one of the evolution visits (week 6, week 12, week 18, week 24, week 30 and week 36), a study will be performed to ascertain whether significant changes have occurred in fatigue-related quality of life versus the previous evaluation, and defined as:

- **Improvement:** if there is an increase of more than 4 points in the FACIT\_Fatigue scale score versus the previous evaluation
- **Maintenance:** if the score on the quality of life scale does not vary by more than 4 points versus the previous evaluation
- **Worsening:** if the score obtained on the Facit\_Fatigue scale decreases by more than four points versus the previous evaluation.

Significant associations will be sought between the habits of daytime rest, the practice of physical aerobic exercise, medication taken, dose and treatment schedule changes, dose interruptions and the number of days of treatment

interruption depending on the evolution in the evaluation of the fatigue in the FACIT\_Fatigue over the last six weeks. The Pearson chi-squared test will be used for this purpose (or Fisher's exact test for 2x2 tables or likelihood ratio test for mxn tables, if necessary).

- Treatment: For each one of the treatment cycles received by patients during the 9-month follow-up, the following will be studied:
  - **Dose change:** the absolute and relative frequency of patients who have changed doses since the last cycle will be provided. In the sub-population of patients with dose changes in the last cycle, their frequency distribution will be presented according to:

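### The weekly exercise item carries a six-month condition and has no option for 1 day, 6 days or sessions under 45 minutes, so diary exposures will be misclassified or missing

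*SAP*

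**What the plan says.** SAP 8.2.3 introduces the diary items with "Patient diary data (weekly): the distribution of patient frequencies will be presented according to the following habits". SAP 6 gives the same frequency for the lifestyle variables: "LIFESTYLE (weekly from baseline visit to month 9".

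- **Exercise.** There are four options: "I have not done any kind of physical exercise"; at least 45 minutes on 2-3 days; "I have done 45 min of physical exercise 4-5 days a week for at least 6 months"; and at least 45 minutes every day. The SAP's own rationale (section 2) says: "Some authors recommend training with aerobic exercises for 30 minutes 3 times a week".
- **Napping.** The options are daily; weekends or holidays; "Sporadically, between 2 or 6 days"; and none.
- **Medication time.** The options are 7 am to noon; 1 to 7 pm; 8 pm to 6 am; and no medication that week. The regimens in SAP 8.2.2 include "Sorafenib 400 mg/12 hours continuous".

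Each habit is then reduced to the option marked most often in the last 12 weeks. It is cross-tabulated against change in fatigue with chi-square, Fisher or likelihood-ratio tests, and compared with the previous visit and with baseline. SAP 7 replaces no missing values. No section says how to code a week that fits no option or two options, a tie over the 12 weeks, or two intake times a day.

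**The concern.** A categorical exposure is usable only if every patient-week fits exactly one category. Here the exercise list fails on coverage, and one category depends on half a year of history rather than on the week being reported. Two patients with identical weeks are then coded differently because of their past. One patient can also change category around month 9 without changing behaviour, and the visit-to-visit comparison would read that as a change in habit.

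At stake are objective 3 (the role of aerobic exercise in the onset of fatigue) and the two parts of objective 4 that come from the diary: napping and time of administration. A patient with no fitting option must tick a wrong one or leave the item blank. Taking the most frequent answer over 12 weeks does not repair an answer that was never available.

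**Working it through.** The plan states no figure on this point to reproduce. The check is whether each option list is exhaustive and exclusive, using the options in SAP 8.2.3, the regimen list in SAP 8.2.2 and the rationale in SAP 2.

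**1. Exercise.** The 4-5 day option is read as 45 minutes or more.

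| Days in week | Under 45 min | 45 min or more, held under 6 months | 45 min or more, held 6 months or longer |
|---|---|---|---|
| 0 | none | none | none |
| 1 | no option | no option | no option |
| 2-3 | no option | 2-3 days | 2-3 days |
| 4-5 | no option | no option | 4-5 days |
| 6 | no option | no option | no option |
| 7 | no option | daily | daily |

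Of the eight day counts, 1, 4 and 6 have an option in the three columns respectively. Thirty minutes three times a week falls in the 2-3 row, first column: no option.

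**2. The six-month condition.** Take six months as 26 weeks, exercise starting with treatment, and an entry as truthful only after 26 completed weeks.

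- Month-3 summary (weeks 1-12): 0 of 12 weeks.
- Month-6 summary (weeks 13-24 or 15-26): 0 of 12.
- Month-9 summary: 10 of 12 if it covers weeks 25-36 (weeks 27 to 36), or 12 of 12 if it covers weeks 28-39.
- Six weeks before each FACIT-Fatigue evaluation: 0 of 6 at weeks 6, 12, 18 and 24; 4 of 6 at week 30; 6 of 6 at week 36.

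Earlier use is truthful only if exercise before treatment counts, which the SAP does not say.

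**3. Napping.** Seven days give 2^7 = 128 patterns, ignoring holidays.

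- Daily: 1. None: 1. Weekend only: 3 (Saturday, Sunday, both).
- Two to six days: 128 - 1 - 7 - 1 = 119.
- The total is 1 + 1 + 3 + 119 = 124, with Saturday plus Sunday counted twice, so 123 distinct patterns are covered.
- 128 - 123 = 5 have no option: a single nap on one weekday.

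Holidays add further overlap.

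**4. Time of intake.** The longest band, 8 pm to 6 am, spans 10 hours to the minute, or 11 whole clock hours. Two intakes exactly 12 hours apart cannot both fall in it, so a 12-hourly regimen normally needs two bands.

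**5. Illustration only.** Assume 95 patients (100 less the planned 5% discontinuation), two equal exposure groups, true worsening of 40% against 20%, two-sided 0.05, and the same misclassification rate m in each direction, unrelated to fatigue. The observed difference is 20 x (1 - 2m) points. For m = 0, 10, 20 and 30% it is 20, 16, 12 and 8 points, and power is 57, 40, 25 and 13%. None of these inputs except the 95 comes from the documents, and the planned tests use more than two categories. This shows how sensitive such a comparison can be; it does not estimate the loss here.

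**The case against.** The study is descriptive, these are secondary association analyses, and the primary FACIT-Fatigue description is untouched. That stands, and it limits the severity.

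The diary form is not in the reviewed text. The range in the napping option may be a translation slip, and Protocol 7.9 concedes that diary data cannot be confirmed and promises site guidelines to standardise their collection. This mitigates only in part: the content of the guidelines is not given, and guidance cannot supply a missing option. The six-month wording may have been meant for a baseline question, since objective 3 also covers exercise before treatment. The SAP nevertheless lists it as a weekly option.

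A reader might infer more than the text supports:

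- **That all three lists overlap.** The exercise options do not overlap each other, nor do the time bands. Overlap is confined to napping and to 12-hourly intake, which affects one of the ten listed regimens, for a drug the SAP describes as uncommon first-line.
- **That 3 of 24 hours of intake are uncoded.** Read to the minute, the bands cover 5 + 6 + 10 = 21 hours. Read as whole clock hours, they cover 6 + 7 + 11 = 24. Either way this is a share of the clock, not of intakes.
- **That half the exercise day counts work for everyone.** Only 0 does; 2, 3 and 7 also need 45-minute sessions.
- **That all of objective 4 is affected.** Treatment breaks and dose reductions are recorded on the CRF (SAP 2.1).
- **That the bias runs toward no effect.** That would need error unrelated to fatigue. Fatigue may influence diary answers and there are more than two categories, so the direction is undetermined.

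**Conclusion.** The defect holds and is clearest for exercise. A weekly item contains a condition that one week cannot establish and that a patient starting exercise with treatment cannot meet before about week 26. No option exists for 1 day, 6 days or any session under 45 minutes, including the pattern cited in the SAP's own rationale. The napping faults are real but small (1 of 128 patterns fits two options, 5 of 128 fit none), and the missing rule for 12-hourly intake is minor.

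Exposures for objective 3, and for napping and administration time in objective 4, will be misclassified or missing to an extent that depends on how patients actually exercise, nap and take their medication. The documents give no such distributions, so neither the amount nor the direction of bias can be calculated. The conclusion assumes that the diary carries the options as the SAP lists them. It warrants correction, at the level of a secondary analysis.

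**What to change.** **If the diary can still be changed:**

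- Take the six-month condition out of the weekly item and ask it once at baseline. Deleting it outright could lose the pre-treatment history that objective 3 needs.
- Record exercise as number of days (0 to 7) and usual minutes per day, and napping as number of days (0 to 7). Analyse days as ordered or continuous variables.
- Make the time bands explicitly contiguous and allow two intake times a day, or leave patients on a 12-hourly regimen out of the time-of-day analysis.

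**If diaries are already in use:**

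- State in the SAP how weeks with no fitting option, weeks that fit two options, and ties over the 12 weeks are coded.
- Treat the 4-5 day option as a frequency only.
- Report that patients with short sessions cannot be recovered. Collapsing to any versus no exercise does not help those who ticked none or left the item blank.

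**Cost.** Rewording of the diary and eCRF, and mapping of data from any diary version already completed. The SAP rules alone are cheap but recover only part of the information.

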## • Has taken the medication:

- In the morning (between 7 am and 12 noon)
- In the afternoon (between 1 pm and 7 pm)
- At night (between 8 pm and 6 am)
- I have not taken any medication this week

For each one of the weekly habits described above, a summary calculation will be made (after three months) of each patient's habits in terms of daytime rest, physical exercise and taking their medication, taking the options marked with greater frequency in the last 12 weeks into account.

FACIT\_Fatigue: The main measures of centrality and dispersion measures will be calculated (mean, standard deviation, median, minimum, maximum, IR and 95%CI ) from the score obtained in the FACIT\_Fatigue quality of life scale, calculated as described in ANNEX 1. The absolute and relative frequency of patients with severe fatigue, being those with a score of less than 30 points on the FACIT\_Fatigue scale, will also be presented.

For each one of the evolution visits (week 6, week 12, week 18, week 24, week 30 and week 36), a study will be performed to ascertain whether significant changes have occurred in fatigue-related quality of life versus the previous evaluation, and defined as:

- **Improvement:** if there is an increase of more than 4 points in the FACIT\_Fatigue scale score versus the previous evaluation
- **Maintenance:** if the score on the quality of life scale does not vary by more than 4 points versus the previous evaluation
- **Worsening:** if the score obtained on the Facit\_Fatigue scale decreases by more than four points versus the previous evaluation.

Significant associations will be sought between the habits of daytime rest, the practice of physical aerobic exercise, medication taken, dose and treatment schedule changes, dose interruptions and the number of days of treatment

interruption depending on the evolution in the evaluation of the fatigue in the FACIT\_Fatigue over the last six weeks. The Pearson chi-squared test will be used for this purpose (or Fisher's exact test for 2x2 tables or likelihood ratio test for mxn tables, if necessary).

- Treatment: For each one of the treatment cycles received by patients during the 9-month follow-up, the following will be studied:
  - **Dose change:** the absolute and relative frequency of patients who have changed doses since the last cycle will be provided. In the sub-population of patients with dose changes in the last cycle, their frequency distribution will be presented according to:
    - Number of dose changes received
      - 1 change \_ New dose
        - Sunitinib 50 mg 4/2 regimen
        - Sunitinib 50 mg 2/1 regimen
        - Sunitinib 37.5 mg 4/2 regimen
        - Sunitinib 37.5 mg 2/1 regimen
        - Sunitinib 25 mg 4/2 regimen
        - Sunitinib 25 mg 2/1 regimen
        - Pazopanib 800 mg/24 hours continuous
        - Pazopanib 400 mg/24 hours continuous
        - Sorafenib 400 mg/24 hours continuous
        - Sorafenib 400 mg/12 hours continuous
      - 2 changes\_ New dose
        - Sunitinib 50 mg 4/2 regimen
        - Sunitinib 50 mg 2/1 regimen
        - Sunitinib 37.5 mg 4/2 regimen
        - Sunitinib 37.5 mg 2/1 regimen
        - Sunitinib 25 mg 4/2 regimen
        - Sunitinib 25 mg 2/1 regimen
        - Pazopanib 800 mg/24 hours continuous
        - Pazopanib 400 mg/24 hours continuous
        - Sorafenib 400 mg/24 hours continuous
        - Sorafenib 400 mg/12 hours continuous
  - **Treatment interruptions:** the absolute and relative frequency of patients who have interrupted the treatment since the last cycle will be given. In

the sub-population of patients with treatment interruptions, their frequency distribution will be presented according to:

- Number of treatment interruptions
  - 1
  - 2
  - 3
  - 4 •
  - 5 •
  - ...
- Total calculation of days of treatment interruption
  - <7 days
  - 7-14 days
  - >14 days

In order to study the evolution of patients in terms of the presence of AEs (HFS and fatigue), patient habits in terms of daytime rest, aerobic physical exercise and taking medication, paired data comparisons will be performed between each one of the visits with the results of the previous visit, as well as of each one of the visits with regard to the results presented at the baseline visit, using, for this purpose, the non-parametric sign tests for categorical variables or the McNemar test in the case of dichotomous variables. In order to ascertain whether there is a significant evolution in the score obtained on the FACIT Fatigue scale throughout the study, comparisons of paired data will be performed for each one of the assessments with regard to the baseline value and with regard to the

previous evaluation using the Student t-test for paired data or the non-parametric Wilcoxon test, as appropriate.

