Although the therapeutic goal in the treatment of metastatic renal cell carcinoma is to prolong the survival of patients, it is equally important to keep treatment-related toxicities as low as possible in order to achieve patient adherence to treatment, thereby maximising dose intensity, which is the determining factor for obtaining better results in the long term. The high incidence of dose reduction and treatment interruptions due to adverse effects could lead to decreased plasma drug exposure and reduced clinical benefit.^{5,6} The drug's tolerability may be a barrier when it comes to maximising the potential efficacy of therapy.

Therefore, maintaining the dose is a challenge, with side effects such as fatigue, diarrhoea, hand-foot syndrome or hypertension. In fact, fatigue and diarrhoea are the most worrying symptoms when questioning patients,¹² to such an extent that 50-75% of patients receiving treatment complains about some degree of asthenia, although only 7-11% of cases interfere with the activities of daily living.

In studies, TKI-related fatigue is highly variable in both degree and duration, although it is generally mild to moderate.¹³ In the case of sunitinib, this is especially significant since this is a drug that is administered intermittently. Fatigue typically occurs 2-3 weeks after the start of treatment, increases in intensity during weeks 3 and 4, and tends to improve during the 2-week off-treatment period, during which patients are comparatively better than during on-treatment weeks. This has resulted in the use of alternate sunitinib scheduling in clinical practice in order to improve tolerability and maintain effective dose intensity, with the schedule of 14 days on and 7 days off being the most commonly used (2/1 schedule). Results based on the use of these schedules by different groups have recently been published (retrospective analyses).^{14,15} The European Association of Urology Guidelines¹⁶ on Renal Cell Carcinoma 2015 describe the

schedule of 2 weeks on and 1 week off treatment for the management of toxicity in patients being treated with sunitinib.

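### The SAP's most-frequent-option rule for medication time counts weeks without drug as an answer, so sunitinib patients reach the no-medication class after shorter interruptions than patients on continuous regimens

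*SAP*

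**What the plan says.** In the diary item on medication intake (SAP 8.2.3) the patient marks, each week, one of three time bands or "I have not taken any medication this week". After three months each habit is summarised per patient by "taking the options marked with greater frequency in the last 12 weeks into account". The text does not limit the count to weeks on treatment, does not separate scheduled rest from unplanned interruption, and has no rule for ties.

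The regimens listed in SAP 8.2.2 differ in exactly this respect. Some are intermittent ("Sunitinib 50 mg 4/2 regimen" and the 2/1 versions), some continuous once daily ("Pazopanib 800 mg/24 hours continuous"), and one is 12-hourly ("Sorafenib 400 mg/12 hours continuous").

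Medication intake is then one of several factors tested, one at a time, by chi-square, Fisher or likelihood ratio tests. SAP section 9 gives it tables against the evolution of hand-foot syndrome (3.1.1), CTCAE fatigue (3.2.3) and FACIT-Fatigue (3.4.3). Regimen and temporary interruptions have separate tables. The 12-week summary is the only per-patient habit variable that the SAP defines, although the FACIT associations look back six weeks.

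**The concern.** Secondary objective 4 treats time of administration as a factor distinct from breaks and dose reductions. A no-medication level inside the timing variable is not a time of day. It stands for some mixture of scheduled rest, interruption and discontinuation.

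That level is also linked to the outcome. The protocol's rationale says that fatigue on sunitinib "tends to improve during the 2-week off-treatment period", and that fatigue itself leads to repeated interruptions. An association in the timing tables could therefore reflect being off drug, or having been tired enough to stop, and the tests do not adjust for either. Because sunitinib patients start with off-weeks already counted, the same break can be classed differently by drug.

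**Working it through.** The SAP states no figure for this rule, so there is none to reproduce. The check applies the rule as written.

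**Inputs.** Protocol section 5 describes a 2-week off-treatment period for standard sunitinib and the 2/1 schedule as 14 days on, 7 off. SAP 8.2.2 lists pazopanib and sorafenib as continuous. The window is 12 weeks (SAP 8.2.3).

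**1. Scheduled off-weeks in 12, diary weeks aligned with cycles.**
- 4/2: (12 / 6) × 2 = 4
- 2/1: (12 / 3) × 1 = 4
- Continuous: 0

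**2. Constant dosing time, with m further diary weeks without a dose.** Sunitinib: timed weeks 8 − m, no-medication weeks 4 + m, equal at m = 2. Continuous: 12 − m against m, equal at m = 6.

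| m | Sunitinib (timed v none) | Continuous (timed v none) |
|---|---|---|
| 0 | 8 v 4, correct | 12 v 0, correct |
| 1 | 7 v 5, correct | 11 v 1, correct |
| 2 | 6 v 6, tie | 10 v 2, correct |
| 3 | 5 v 7, no medication | 9 v 3, correct |
| 6 | 2 v 10, no medication | 6 v 6, tie |
| 7 | 1 v 11, no medication | 5 v 7, no medication |

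**3. Split dosing times on sunitinib, no interruption.** Eight on-weeks fall into three bands in 45 ways. The no-medication count of 4 wins outright only for 3/3/2 (3 orderings). It ties for first place in 12: 4/4/0 (3), 4/3/1 (6) and 4/2/2 (3).

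**4. Alignment.** If off-blocks are shifted 1 to 6 days against the diary week, whole weeks without drug fall to 2 in 12 on 4/2 and 0 on 2/1. For 4/2 the count becomes 10 − m against 2 + m: tie at m = 4, no medication at m = 5. For 2/1 the thresholds equal those of a continuous regimen.

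**5. Variable timing (illustration, aligned weeks).** Let p be the share of on-weeks at the usual time; the documents give no value. With no interruption the usual band wins outright if it has at least 5 of 8 on-weeks. With one interrupted week it needs at least 6 of 7. The last two columns assume that the remaining weeks split equally between the other two bands.

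| p | SAP rule, sunitinib, no interruption | SAP rule, sunitinib, 1 interrupted week | SAP rule, continuous, no interruption | On-weeks only, 8 weeks |
|---|---|---|---|---|
| 0.9 | 99.5% | 85.0% | 100.0% | 99.9% |
| 0.8 | 94.4% | 57.7% | 99.7% | 98.4% |
| 0.7 | 80.6% | 32.9% | 97.5% | 92.5% |
| 0.6 | 59.4% | 15.9% | 89.1% | 79.7% |

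Entries are the probability that the usual time is the unique most frequent option. Much of the shortfall under the SAP rule is ties: at p = 0.7 with one interrupted week, 35.0% are classed as no medication and 32.0% tie with it.

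**6. Six-week window.** If the same rule were shortened for the FACIT tables, sunitinib gives 4 − m against 2 + m (tie at 1, no medication at 2). Continuous gives 6 − m against m (tie at 3, no medication at 4).

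**The case against.** The best defence is that the schedule alone does no harm. A sunitinib patient who doses at a constant time and has no interruption is classed correctly, 8 against 4. A reader might infer that timing is confounded with regimen for sunitinib patients in general; the arithmetic does not support that. It takes further interrupted weeks or divided dosing times.

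Three other inferences also go too far:
- **That misclassification will be common.** The protocol cites temporary interruption in 38% of patients in the pivotal sunitinib trial, but gives no duration. It does not show how many would miss 2 or 3 whole diary weeks within 12.
- **That any break would appear as a change of dosing time in the paired comparisons at the end of SAP 8.2.3.** Only a break long enough to change the most frequent option would do so, and only if those comparisons use the 12-week summary, which the SAP does not say.
- **That 12-hourly sorafenib cannot be recorded.** The diary is not among the documents, and the plural wording of the rule may allow more than one mark per week. If so, the two bands would tie, and no rule resolves that. The protocol also says first-line sorafenib is not very common, so few patients are involved.

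It is fair, too, that this is one derived covariate for a secondary objective in a study described as descriptive. The FACIT-Fatigue scores do not depend on it.

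What remains is that no text excludes weeks without drug from the count, and that the break length at which the class changes can depend on regimen.

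**Conclusion.** The concern holds in a limited form. As written, the rule can place a patient in a no-medication class within the timing tables. With aligned diary weeks and a constant dosing time, the thresholds are 2 weeks (tie) and 3 weeks (reclassified) on sunitinib, against 6 and 7 on a continuous regimen. Full adherence with a 3/3/2 split gives the same class. The timing variable can therefore mix time of day with interruption and regimen in unadjusted tests.

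The gap between regimens narrows on 4/2, and disappears on 2/1, if diary weeks do not align with cycles. The size of any bias cannot be computed from the documents, because interruption length and timing variability are not given; the probabilities above are illustrations under assumed values of p. The rule should be corrected before the association tables are produced.

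**What to change.** In SAP 8.2.3:
- Derive time of administration as the most frequent band among weeks with at least one dose, and set it to missing if there is no such week. A patient with a constant time is then classed correctly whatever the breaks.
- Keep the no-medication weeks for the analyses of interruptions and of off-treatment periods. The latter are a named factor in protocol objective 4 but absent from objective 4 in SAP 2.2.
- State a tie rule, for example a mixed class; a 4/4 split still ties after the change.
- Use a matching six-week window for the FACIT associations.
- Code 12-hourly regimens as twice daily and leave them out of the time-of-day comparison.
- Report the timing associations by regimen, intermittent against continuous.
- If the paired comparisons use this variable, apply the same derivation and compare on-treatment visits only, since baseline precedes treatment and has no dosing time.

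The cost is SAP wording and a re-derived variable from diary and regimen data already collected. Sunitinib patients contribute fewer weeks to the summary, and the few twice-daily patients leave the timing comparison.
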